Integrated Alcohol Disorder and PTSD Treatment

NCT01601067

04/14/2016

Objectives

The primary aim will be to evaluate the effects on alcohol use and PTSD symptoms of an exposure-based integrated AD and PTSD intervention (i.e., COPE) when compared to a present-focused coping skills intervention (i.e., Seeking Safety [SS]) in male and female Veterans with comorbid AD and PTSD. Hypotheses for the primary aim are:

1. At post-treatment, both groups will show reductions in alcohol use, but COPE will demonstrate greater reduction in PTSD symptoms than SS.
2. At the 2nd and 3rd post treatment follow up assessment ,COPE will have significantly fewer percent drinking days than SS.
3. At the 2nd and 3rd post treatment follow up assessment ,COPE will continue to have lower PTSD symptom scores.

Design.

The proposed study will be a randomized controlled trial comparing Concurrent Treatment of PTSD and Substance Use Disorders using PTSD (COPE) to Seeking Safety (SS) for the treatment of male and female Veterans with AD/PTSD. 178 participants will be enrolled through the San Diego VA and randomized at the individual level. Measures will occur at baseline, post-treatment, and two post treatment follow up assessments. Participants will complete the 2nd post treatment assessment interview and set of questionnaires 3 months after the 1st post treatment appointment. Participants will be scheduled for their 3rd and last post treatment interview 3 months after completing their 2nd post treatment assessment. All procedures will be done for research purposes.

Methods

All work will be carried out at the SAMI outpatient program and PTSD clinics of the Veteran Affairs San Diego Healthcare Systems (VASDHS). Random permuted blocks will be used which ensure exactly equal treatment numbers at certain equally spaced points in the sequence of patient assignment. Randomization will be stratified by gender to ensure a balanced number of males and females are in each treatment group.

The Timeline Follow-back Procedure (TLFB50) will be employed at baseline, post-treatment, 5-month, and 8-month follow up to evaluate drinking and all drug use during the 30 days preceding each interview.

The Clinician-Administered PTSD Scale for DSM-V(CAPS54,55) is a standard semi-structured interview used to assess PTSD diagnosis and severity. As part of the CAPS, a list of potentially traumatic events is given to respondents.

Eligible participants will contact our study in response to flyers/ brochures posted in San Diego VA hospital, including the Mission Valley, Chula Vista, and Oceanside CBOCS; and by referral from VA primary care, substance use mental illness (SAMI), PTSD (OEF/OIF/OND, PCT, MST), and other clinics (ADTP, SARRTP); and also from VASDHS and VMRF websites under "Research opportunities"

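### Balance at regular intervals implies a fixed block length and no concealment is described; if enrolling staff know the length and see the sequence, a fifth to a third of allocations are certain in advance

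*Protocol*

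**What the plan says.** The Protocol's Methods section gives the allocation rule in two sentences: "Random permuted blocks will be used which ensure exactly equal treatment numbers at certain equally spaced points in the sequence of patient assignment" and "Randomization will be stratified by gender to ensure a balanced number of males and females are in each treatment group". The Design section gives the size and unit: "178 participants will be enrolled through the San Diego VA and randomized at the individual level". The Methods section places all work in the SAMI programme and PTSD clinics of a single VA healthcare system. The Objectives describe an exposure-based treatment "when compared to a present-focused coping skills intervention".

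Neither document gives a block length, says that lengths vary, says who generates or holds the list, says when an assignment is released, or describes who is masked. The SAP does not discuss randomisation.

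**The concern.** If balance is exact at regular intervals, the natural reading is a constant block length. Anyone who knows that length and has followed the assignments within a gender can tell when one arm's places in the current block are used up. Every remaining assignment in that block is then known before the next patient is enrolled.

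Two openly different talking therapies cannot be disguised from those who deliver them, so past assignments are not hidden by the nature of the treatments. What would protect the sequence is procedure, and none is described.

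The stake is selection at entry. Knowledge of the next arm could influence who is put forward, when they are enrolled, or how a baseline interview is scored. The primary tests in SAP section 6.H.3 are treatment-by-time interactions that start from baseline, so any such influence would enter the contrast directly. The SAP's missing-at-random and pattern-mixture analyses deal with missing outcomes and would not reliably correct for it.

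**Working it through.** **Inputs.** From the Protocol: permuted blocks with regular balance points, equal allocation (hence 1:1), stratification by gender, 178 randomised. Assumed, because the documents do not say: block length (2 to 10, with 4, 6 and 8 as the main cases) and share of women (5% to 50%). The plan gives no predictability figure to reproduce.

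**1. Known fixed length.** For a 1:1 block of length 2m:

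- Share certain in advance = 1/(m + 1).
- Share guessed correctly by always naming the arm that is behind = [m + (4^m / C(2m, m) − 1)/2] / (2m).

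Hand check for length 4 (m = 2). Up to swapping the arms, the sequences are AABB, ABAB and ABBA. They contain 2, 1 and 1 forced assignments: 4 of 12, or 1/3. Expected correct guesses are 2.5, 3 and 3: 8.5 of 12, or 70.8%. The formula gives [2 + (16/6 − 1)/2]/4 = 70.8%.

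| Block length | Certain in advance | Best guess correct |
|---|---|---|
| 2 | 1/2 = 50.0% | 75.0% |
| 4 | 1/3 = 33.3% | 70.8% |
| 6 | 1/4 = 25.0% | 68.3% |
| 8 | 1/5 = 20.0% | 66.6% |
| 10 | 1/6 = 16.7% | 65.3% |

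Without any information the figures would be 0% and 50%.

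**2. Counts in this trial.** Simulating 178 participants in two gender strata, with incomplete last blocks and 9, 18, 36 or 89 women, gives 58.6 to 58.7 certain assignments for length 4, 42.9 to 43.9 for length 6, and 33.6 to 35.4 for length 8. In round figures these are 59, 44 and 35. The gender split hardly matters.

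**3. Fixed length, not disclosed.** Suppose an observer sees one sequence of 178 in order and infers the length by Bayes' rule from 2, 4, 6, 8 or 10. The observer is 95% sure of the true length after a median of 20 to 39 assignments (true lengths 2 to 8). For lengths 4, 6 and 8, that observer can call 25.7%, 20.5% and 17.5% of assignments with over 99% probability. Secrecy reduces the problem but does not remove it.

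**4. Lengths varied at random.** The observer is allowed to know the set of lengths and to see every past assignment:

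| Lengths | Certain in advance | Best guess correct |
|---|---|---|
| 4, 6 | 5.4% | 69.3% |
| 4, 8 | 7.5% | 67.8% |
| 4, 6, 8 | 2.3% | 68.0% |

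For 4, 6 and 8 that is 0.023 × 178, or about 4 participants. The 2.3% counts strictly certain assignments, so it should be compared with the 33%, 25% and 20% in step 1; step 3 uses a looser threshold. Best-guess accuracy is about that of a fixed length of 6 and slightly higher than that of a fixed length of 8.

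**The case against.** The strongest reply is that fixed blocks are a common choice, that withholding the length from a protocol is good practice, and that nothing here shows anyone could exploit the sequence. Recruitment runs through flyers, websites, primary care, several specialty programmes and outlying clinics, and no single referrer is shown to see assignments in order. A therapist who knows a patient's arm does not thereby know the ordered list within gender. This stands: the exposure is conditional, and concealment may be specified in a procedure that is not part of these short documents.

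It can also be said that the sentence merely describes what permuted blocks do, and that regular balance points do not strictly force a constant length. Blocks of 4 and 8 in random order within each run of 12 would balance at 12, 24, 36 and so on. That is correct, so the fixed length is implied rather than stated. Such a nested scheme is contrived, however, and nothing in the text suggests it.

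Two further inferences are tempting but unsupported. One is that the smaller gender stratum is easier to follow. The simulated shares barely change from 5% to 50% women, and a stratum of 9 gives too few assignments to learn an undisclosed length from that stratum alone. The other is that block length bears on the PTSD outcome because the CAPS "is a standard semi-structured interview used to assess PTSD diagnosis and severity". How follow-up interviews are scored is a matter of assessor masking, which changing the blocks would not address.

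Finally, varying the lengths leaves best-guess accuracy almost unchanged. That also stands, and it is why the remedy cannot consist of varied lengths alone.

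**Conclusion.** The point holds as a conditional design weakness. The wording implies a constant block length, and no concealment is described. If enrolling staff both know the length and see earlier assignments in order within gender, a fifth to a third of allocations are certain in advance for lengths 4 to 8. Over lengths 2 to 10 the share runs from 50% down to 17%.

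A reader might infer that staff in this trial can in fact foresee a large share of allocations. The documents do not support that: they do not say what the length is, whether it is disclosed, who enrols, or who sees past assignments. The conclusion also assumes that blocking is done separately within each gender, which is the natural reading but is not spelled out.

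This is a cheap improvement to the plan, not evidence of bias.

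**What to change.** Replace the block sentence in the Protocol's Methods with one that specifies:

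- permuted blocks of randomly varied length (for example 4, 6 and 8) within each gender stratum;
- lengths not disclosed to study or clinic staff;
- a list generated and held by someone not involved in enrolment;
- release of each assignment only after eligibility and baseline CAPS and TLFB are recorded.

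If randomisation has already begun, record the scheme in use and who holds the list, and apply the change to the remaining assignments.

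The cost is one line in the randomisation program and a few protocol sentences. The downside is that exact balance no longer falls at regular points. If enrolment stops inside a block of 8, one stratum can be out of balance by at most 8/2 = 4 participants, so by at most 2 × 4 = 8 over both strata.

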Integrated Alcohol Disorder and PTSD Treatment

NCT01601067

09/03/2011

Primary Outcome Analyses.

6.H.3. Primary Outcome Analyses. The first primary aim is to evaluate if I-PE will demonstrate greater reduction in PTSD symptoms than SS at post treatment. The statistical model will be a random intercept regression model with treatment condition (I-PE, SS) and a linear term for time (0, 2 months). The primary test of the treatment conditions will be treatment x time interaction effect. We will also test the extent to which gender moderates treatment effect. The model can be expanded to determine an adjusted intervention effect by including additional covariates(e.g., age, ethnicity). This model provides maximum likelihood (ML) parameter estimates; allowing modeling of the covariance error structure data across assessment points.⁹¹

The second primary aim is to evaluate if I-PE will result in greater percent days abstinent (PDA) from substance use at 5 and 8-month follow-up. The statistical model will be a random intercept regression model with treatment condition (I-PE, SS) and a linear term for time (0, 2, 5, 8 months). The primary test of the treatment conditions will be the treatment x time interaction effect. A quadratic effect of time will also be tested to model potential decaying treatment effects. We will test the moderating effect of gender on the treatment effect by testing a treatment x time x gender interaction term in the model. Additional covariates can also be added to the model to determine an adjusted intervention effect.

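### Randomisation is stratified by gender, but the SAP specifies the primary treatment x time tests without gender terms; adding gender and gender x time would be a small, nearly free gain

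*Protocol*

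**What the plan says.** The protocol (Methods) names one stratification factor: "Randomization will be stratified by gender to ensure a balanced number of males and females are in each treatment group". Allocation is by permuted blocks: "Random permuted blocks will be used which ensure exactly equal treatment numbers at certain equally spaced points in the sequence of patient assignment". Block size is not given. Planned size: "178 participants will be enrolled through the San Diego VA and randomized at the individual level".

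SAP section 6.H.3 defines the first primary model, for PTSD symptoms, as "a random intercept regression model with treatment condition (I-PE, SS) and a linear term for time (0, 2 months". It continues: "The primary test of the treatment conditions will be treatment x time interaction effect". Gender comes after that: "We will also test the extent to which gender moderates treatment effect". Covariates may be added for an adjusted effect; the two examples given are age and ethnicity.

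The second primary model, for PDA, has the same form with assessments at 0, 2, 5 and 8 months. It has a random intercept and no random slope, and treatment x time is again the primary test. On gender the SAP says: "We will test the moderating effect of gender on the treatment effect by testing a treatment x time x gender interaction term". The sentence ends by placing that term within the model. Further covariates are optional and unnamed.

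Neither document gives the expected share of women, any expected gender difference in change, an alpha level or a power calculation.

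**The concern.** Stratified blocks keep the arms close to balanced within each gender. Any gender difference in change then largely cancels from the treatment comparison, and the true sampling error falls. A model without gender does not credit this: it counts the difference between men's and women's mean change as residual variation. The reported standard error is then larger than the true one, the interval is too wide and the test is conservative. Part of the precision that stratification bought is lost.

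Because the primary test concerns change over time, the term that matters is gender x time. With a random intercept and complete data, a gender difference in level alone leaves the treatment x time standard error essentially unchanged, so a gender main effect by itself would not help.

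Clarity is also at stake. If the three-way term sits in the model that supplies the primary PDA estimate, and gender is coded 0/1, the treatment x time coefficient is the effect in the reference gender rather than in all participants.

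**Working it through.** **Inputs from the documents.** 178 participants, or 178/2 = 89 per arm if equal; gender-stratified permuted blocks; PTSD model at 0 and 2 months; PDA model at 0, 2, 5 and 8 months; random intercept only. There is no stated figure on this point to reproduce.

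**Assumed, because not in the documents.** Share of women p from 0.1 to 0.5; gender difference in mean change d from 0 to 0.8 within-gender SDs of change; two-sided alpha of 0.05; complete data; near-exact balance within gender; 80% power in the gender-adjusted analysis.

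**PTSD model.** With two time points and complete data, treatment x time is the arm difference in mean change (per unit time). Let s^2 be the within-gender variance of change.

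- Variance of change when gender is ignored: s^2(1 + p(1-p)d^2).
- Variance that drives the true sampling error under balance within gender: s^2.
- Reported SE / true SE: k = sqrt(1 + p(1-p)d^2).
- Actual type I error: 2(1 - Phi(1.96k)).
- Power: Phi(1.96 + 0.8416 - 1.96k).

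Example, p = 0.5 and d = 0.5: k = sqrt(1 + 0.25 x 0.25) = sqrt(1.0625) = 1.0308. Type I error = 2(1 - Phi(2.020)) = 4.3%. Power = Phi(2.8016 - 2.0204) = Phi(0.781) = 78.3%.

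| Women | d | k | SE overstated | Type I error | Power |
|---|---|---|---|---|---|
| any | 0 | 1.000 | 0% | 5.0% | 80.0% |
| 10% | 0.2 | 1.0018 | 0.2% | 4.96% | 79.9% |
| 50% | 0.2 | 1.0050 | 0.5% | 4.89% | 79.7% |
| 10% | 0.5 | 1.0112 | 1.1% | 4.75% | 79.4% |
| 50% | 0.5 | 1.0308 | 3.1% | 4.34% | 78.3% |
| 10% | 0.8 | 1.0284 | 2.8% | 4.38% | 78.4% |
| 50% | 0.8 | 1.0770 | 7.7% | 3.48% | 75.5% |

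A simulation (178 participants, stratified blocks of 4 assumed, 8,000 runs per setting) agrees: the unadjusted reported SE is 1.011 to 1.078 times the adjusted one for d of about 0.5 to 0.8.

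**PDA model.** The same formula does not apply. The simulation was repeated at four time points, with men and women differing in 8-month change by 0.7 or 1.13 residual SDs, and with 10% or 50% women.

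- No individual slope variation: reported/true SE of the unadjusted test is about 1.00 to 1.03.
- Individual slopes varying (SD of total 8-month change from slope of 0.5 to 1.0 residual SD): reported/true SE is 0.87 to 0.99 and type I error 5.5% to 9.0%.
- Same settings with gender x time added: ratio 0.86 to 0.96, type I error 5.9% to 9.4%.

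Gender x time lowers the reported PDA standard error by about 0.4% to 3%, but does not make it correct when slopes vary.

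**Reference-gender coding.** With the three-way term in the model and gender coded 0/1, treatment x time rests on one gender. At 20% women (assumed), its SE relative to the overall effect is 1/sqrt(0.8) = 1.12 with men as reference and 1/sqrt(0.2) = 2.24 with women as reference.

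**The case against.** Three objections carry weight.

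First, the SAP does not ignore gender. It plans a gender test for each aim, and a conventional model containing treatment x time x gender also contains gender and gender x time. For PDA, therefore, the text does not show that the primary estimate excludes gender; it leaves the matter open. The covariate examples are only examples and do not rule gender out. This stands, and it limits the PDA part to a request for clarity. For PTSD symptoms the primary test is stated before gender is mentioned, so the omission is plainer. In neither case does a moderation test amount to an adjusted primary analysis.

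Second, a reader might infer that both primary tests are conservative whenever men and women change differently. The documents do not support that for PDA. That model has no random slope, and ordinary variation between individuals in slope can push its standard error below the truth by more than the gender effect pushes it up.

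Third, the effect is small and rests on assumed inputs. This also stands. For gender differences up to 0.5 SD the overstatement never exceeds about 3%, and at 10% women it is about 1%.

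**Conclusion.** The point holds as a minor matter of efficiency and clarity. The trial randomises within gender, but the primary tests as written do not analyse by it. In the PTSD model with complete data, the cost at d = 0.5 is a standard error 1.1% to 3.1% too large and power of about 78% to 79% instead of 80%. At d = 0.2 it is negligible, and with no gender difference it is nil. The upper figure of 7.7% needs both a 0.8 SD difference and equal numbers of men and women, and nothing in the documents supports either.

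The treatment estimate is unbiased, and in the PTSD model the departure from nominal type I error is on the safe side. Anyone tempted to read this as a threat to the validity of the primary conclusions would be going further than the documents allow. For PDA no direction can be claimed: whether its standard error is too large or too small depends mainly on individual slope variation, which is a separate matter.

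**What to change.** State in SAP section 6.H.3 that both primary models include gender and gender x time as fixed effects; that treatment x time, from a model without the three-way term, is the primary test; and that treatment x time x gender is fitted only in a separate moderation model. The primary coefficient is then an overall effect, not the effect in one reference gender.

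The cost is a sentence or two and two degrees of freedom per model in 178 participants. Gender is known for everyone at randomisation, so no data are lost. If men and women change alike, nothing material is gained or lost.

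This does not correct the PDA standard error if individual slopes vary. In the simulated cases with slope variation, removing the gender component left the test slightly further above 5%, so the covariance structure of the PDA model should be settled at the same time.

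### The primary drinking analysis names no prognostic covariate, although baseline CAPS severity is collected; prespecifying it with its time interaction would buy a small gain in precision at almost no cost

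*Protocol*

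**What the plan says.** For the second primary aim, SAP 6.H.3 states: "The statistical model will be a random intercept regression model with treatment condition (I-PE, SS) and a linear term for time (0, 2, 5, 8" (times are in months). It goes on: "The primary test of the treatment conditions will be the treatment x time interaction effect". A quadratic time effect and a treatment x time x gender term will also be tested. On other baseline variables there is one permissive sentence: "Additional covariates can also be added to the model to determine an adjusted intervention effect". None is named for this outcome. Age and ethnicity are given as examples, but in the paragraph on PTSD symptoms.

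The SAP's missing-data text asks for variables related to missingness to be in the model. Its candidates are group assignment, social and familial support, employment status and income. Neither PTSD severity nor referral source is among them.

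On design, the Protocol says "178 participants will be enrolled through the San Diego VA and randomized at the individual level", and "Randomization will be stratified by gender to ensure a balanced number of males and females are in each treatment group". Gender is the only stratification factor given. The CAPS "is a standard semi-structured interview used to assess PTSD diagnosis and severity". The Design section places measures at baseline, and the SAP's PTSD model has a time-0 value, so baseline severity should exist for everyone randomised.

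The recruitment text lists flyers, websites and entry "by referral from VA primary care, substance use mental illness (SAMI), PTSD (OEF/OIF/OND, PCT, MST), and other clinics (ADTP, SARRTP"). It does not say that the route is recorded for each participant.

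**The concern.** Treatment x time is a difference in change. A random intercept absorbs stable differences between people in how much they drink. It does not absorb differences in how their drinking moves over the 8 months. If baseline PTSD severity predicts that movement, which is plausible in a trial built on the link between the two disorders, the predictable part stays in the sampling variance of the tested effect, and the trial gives up precision it could have had from a value it already collects.

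The second stake is the choice of analysis. With covariates optional and unnamed, the plan does not fix which adjusted estimate will be shown beside the primary test.

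**Working it through.** **Inputs from the documents.** N = 178, randomised individually. Permuted blocks imply equal arms, taken as 89 each. Visits are at 0, 2, 5 and 8 months: mean 3.75, sum of squared deviations 36.75 per person. The tested quantity is the difference in slopes. No alpha, power, effect size, standard deviation, correlation or dropout rate is given, so 178 cannot be reproduced and the size of any gain rests on assumption.

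**Formulas.** If a covariate's interaction with time explains a share R² of the between-person variance in change, the standard error (SE) is multiplied by √(1 − R²), and the gain is worth 178/(1 − R²) − 178 participants. For one continuous covariate, R² = r².

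**Baseline CAPS, r assumed.**

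| r with change in PDA | R² | SE factor | SE cut | Participants' worth |
|---|---|---|---|---|
| 0 | 0 | 1 | 0 | 0 |
| 0.1 | 0.01 | √0.99 = 0.995 | 0.5% | 178/0.99 − 178 = 1.8 |
| 0.2 | 0.04 | √0.96 = 0.980 | 2.0% | 178/0.96 − 178 = 7.4 |
| 0.3 | 0.09 | √0.91 = 0.954 | 4.6% | 178/0.91 − 178 = 17.6 |

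**Referral source, illustration only.** R² = share × (1 − share) × gap² / SD², where share is the proportion from substance-use programmes and gap is their difference in mean change from the rest.

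- 25% share, 30-point gap, SD 40: 0.1875 × 900 / 1600 = 0.105; SE factor 0.946; 178/0.8945 − 178 = 21.
- Same share and SD, 15-point gap: 0.1875 × 225 / 1600 = 0.026; SE cut 1.3%; about 5 participants.
- Over shares of 15% to 35%, gaps of 15 to 45 points and SDs of 35 to 40, the SE cut runs from 1% to 21%. A range that wide reflects the assumptions, not the trial.

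**Does the form of adjustment matter?** The SAP's random-intercept model was simulated with 178 people and 150 replicates per scenario. Assumed values: residual SD 20, unexplained slope SD 1.5 per month, and slope effects per SD of 1.0 for severity and 0.7 for source. The table gives the empirical SD of the treatment x time estimate.

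| Scenario | No covariates | Main effects only | Covariate x time |
|---|---|---|---|
| Covariates predict slope, complete data | 0.613 | 0.613 | 0.588 |
| Same, 30% of follow-up visits missing at random | 0.664 | 0.648 | 0.602 |
| Covariates do not predict slope, complete data | 0.563 | 0.563 | 0.564 |

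Main effects alone change nothing with complete data. Interactions with time cut the SD by about 4% (0.588/0.613 = 0.959), or about 9% with missing visits (0.602/0.664 = 0.907). These cuts are for severity and source together. Each SD carries a Monte Carlo error of about 1/√300 = 6%, but the three fits in a row use the same data sets.

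**Analytic check, complete data.** Slope variance is 400/36.75 + 1.5² + 1.0² + 0.7² = 14.62, of which the covariates explain 1.49 (R² = 0.10). The true SE is √(14.62 × 2/89) = 0.573 without them and √(13.13 × 2/89) = 0.543 with them, a cut of 5%. This agrees with the simulation within its error.

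**The case against.** The strongest reply is that an unadjusted primary test, with an adjusted version beside it, is legitimate in a randomised trial, and that the SAP does allow for covariates. This stands: the plan does not ignore them. What is missing is a named, prespecified choice.

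A reader might infer that leaving out these variables biases the drinking result. It does not. Chance imbalance in severity or source is part of the same sampling variability that the SE describes, not a second harm.

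A reader might also infer that the trial holds referral source as a baseline variable and that adjusting for it would bring the larger gains. The Protocol lists recruitment routes only. Routes can overlap, since a clinic patient may answer a flyer, and arriving through a substance-use clinic does not show that someone is already drinking little. If room to improve is the mechanism, baseline drinking on the Timeline Follow-back measures it directly, and source would add less once baseline drinking is adjusted for.

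A further objection is that the model's reported SE is the greater worry. With slopes that vary and no random slope, the simulated mean reported SE was 0.519, against an empirical SD of 0.613 and an analytic value of 0.573. The reported interval would then be too narrow. Covariate x time terms move the reported SE only from 0.519 to 0.512. This stands as a separate and larger issue, and the adjustment proposed here does not cure it.

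**Conclusion.** The point holds as a minor improvement. The primary drinking model prespecifies no prognostic covariate although baseline CAPS severity is collected, and any slope difference that severity predicts is left in the sampling variance of treatment x time. The supportable size is the CAPS figure: a 0.5% to 4.6% cut in the SE, or about 2 to 18 participants' worth on 178, for assumed correlations of 0.1 to 0.3 with change in PDA. It is nil at zero correlation, and the documents do not indicate where in that range the truth lies. The figures also assume that baseline drinking is not itself adjusted for. The referral-source figures are illustrative and should not be used to argue for the change.

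**What to change.** In SAP 6.H.3, second primary aim, replace the permissive covariate sentence with a commitment: the primary drinking model includes baseline CAPS severity (continuous, measured before randomisation) and its interaction with time, and treatment x time is tested in that model. Add referral source and source x time only if source is recorded for every participant before randomisation, with categories fixed in advance. If the sponsor prefers an unadjusted primary test, say so and name the covariates of the adjusted version.

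The cost is a sentence or two of SAP text and a degree of freedom or two for CAPS, negligible at 178. No new data are needed for the CAPS part. For the true gain to show in the reported interval, the model must also allow slopes to vary between people; that should be settled separately.
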